12.4 Statistical Analysis Plan

In general, data will be summarized by using counts and percents for discrete parameters, and by descriptive statistics (number of observations, mean, standard deviation, median, minimum and maximum) for continuous parameters. Response rates will be calculated as the percent of evaluable patients that have confirmed CR by radiographic response including CT and/or PET scans; 95% Clopper Pearson confidence limits will be calculated for this estimate. Toxicity information recorded will include the type, severity, and the probable association with the study regimen. Tables will be constructed to summarize the observed incidence by severity and type of toxicity. Baseline information (e.g., the extent of prior therapy) and demographic information will be presented as well to describe the patients treated in this study. Time to response and survival endpoints will be estimated using the product-limit method of Kaplan and Meier. The

cumulative incidence of relapse/progression and non-relapse mortality will be calculated as competing risks using the method of Gooley et al¹⁷.

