11.1 Definitions

Evaluable for toxicity: All participants will be evaluable for toxicity from the time of their first treatment with nivolumab.

Evaluable for objective response: Only those participants who have measurable disease present at baseline, have received at least 4 weeks of therapy, and have had their disease re-evaluated will be considered evaluable for response. These participants will have their response classified according to the definitions stated below.

Duration of overall response: The duration of overall response is measured from the time measurement criteria are met for CR or PR, per 2014 Lugano Criteria,¹⁶ (whichever is first recorded) until the first date that relapsed or progressive disease is objectively documented.

Duration of overall CR: The duration of overall CR is measured from the time measurement criteria are first met for CR until the first date that progressive disease is objectively documented.

Duration of stable disease: Stable disease is measured from the start of the treatment until the criteria for progression are met, per 2014 Lugano Criteria,¹⁶ taking as reference the smallest measurements recorded since the treatment started, including the baseline measurements.

Overall Survival (OS): OS is defined as the duration of time from start of treatment to time of death (due to any cause).

Progression-Free Survival (PFS): PFS is defined as the duration of time from start of treatment to time of progression or death, whichever occurs first.

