11.2 Transplant Endpoint Definitions

Overall Survival (OS): OS is defined as the duration of time from start of AHCT treatment to time of death (due to any cause). Evaluated and recorded at day 30, day 100, 6 months, 1-year and 2-years post HCT.

Progression-Free Survival (PFS): PFS is defined as the duration of time from start of HCT treatment to time of progression or death, whichever occurs first. Evaluated and recorded at day 30, day 100, 6 months, 1-year and 2-years post HCT.

Relapse/Progression (CIR): The event is relapse/progression. The time to this event is measured from start of HCT treatment. Deaths without relapse/progression are considered a competing risk. Surviving patients with no history of relapse/progression are censored at time of last follow-up. Evaluated and recorded at day 30, day 100, 6 months, 1-year and 2-years post HCT.

Non-relapse mortality (NRM): NRM is defined as death occurring in a patient from causes other than relapse or progression. NRM is measured from start of treatment until non-disease related death, or last follow-up, whichever comes first. Deaths from relapse/progression are considered a competing risk. Evaluated and recorded at day 30, day 100, 6 months, 1-year and 2-years post HCT.

11.2.1 Toxicities and Adverse Events:

The worst grade of all toxicities will be collected from start of conditioning to day -1, and again from day 0 to 30 post-transplant. From day 31 to 100 post-transplant toxicities that are considered serious adverse events will be collected. Toxicity will be assessed and reported using the CTCAE v4.03 scale.

Stem cell mobilization: mobilization regimen used, median number of cells collected, median number of days to reach minimum collection.

Engraftment (Recovery of Granulopoiesis and Megakaryopoiesis): Engraftment will be assessed using two distinct milestones: 1) ANC (neutrophils) $\geq 0.5 \times 10^3/\mu\text{L}$ achieved and sustained for 3 consecutive lab values on different days with no subsequent decline; and 2) Platelets (PLT) $\geq 20 \times 10^3/\mu\text{L}$ independent of platelet transfusion support. For platelet recovery, date should reflect no transfusions in previous 3 days and the first of 3 consecutive lab values on different days.

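### Time to response is assigned to Kaplan-Meier with no competing event, and response duration does not count death; both summaries can be optimistic if patients who fail or die are censored

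*Combined protocol and SAP*

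**What the plan says.** Section 12.4 gives the estimator: "Time to response and survival endpoints will be estimated using the product-limit method of Kaplan and Meier". The synopsis says the same. Section 12.4 reserves competing-risks estimation for two endpoints, relapse/progression and non-relapse mortality.

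Section 11.1 runs duration of overall response "until the first date that relapsed or progressive disease is objectively documented". Duration of CR runs from when the criteria are "first met for CR until the first date that progressive disease is objectively documented". Neither names death. In the same section, "PFS is defined as the duration of time from start of treatment to time of progression or death, whichever occurs first".

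Section 11.2 handles death explicitly, but only for transplant endpoints. For post-transplant relapse, "Deaths without relapse/progression are considered a competing risk" and "Surviving patients with no history of relapse/progression are censored at time of last follow-up".

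Response duration is a secondary objective in both cohorts (Sections 1.2 and 1.4.2). Time to response appears in no objective and is not defined. No section states its analysis set or how death, withdrawal or new therapy before response is handled. No estimator is named for response duration.

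**The concern.** Kaplan-Meier has two states, event or censored, and assumes that a censored patient keeps the same future chance of the event as those still at risk. A patient who has died or has left protocol therapy without responding can no longer respond on study. Censoring that patient pushes the curve above the proportion who actually respond. Such exits are foreseeable: Section 5.3 lists progression, adverse events, non-compliance and withdrawal as reasons to stop, and Section 7.2 takes patients off trial after a 14-day NIVO + ICE delay.

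Duration raises a related question. Responders are bridged to transplant, and the plan expects to estimate non-relapse mortality. A death in remission is not an event under Section 11.1, so an ordinary Kaplan-Meier analysis would censor it. At stake is how the speed and durability of response are reported, not the test of the regimen.

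**Working it through.** The plan gives no figure for either summary, so there is none to reproduce. The calculations below show size only, and the event counts and rates are assumptions.

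**Time to response (Cohort A)**

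From the documents: n = 43 (Section 12.1.1) and scans at the end of weeks 6, 12 and 18 (Section 10.1, footnote f). Assumed: first CRs of 15, 10 and 5 at those scans. The total of 30/43 = 69.8% sits at the plan's 70% promising rate. Also assumed: exits without CR split equally after weeks 6 and 12, and censored.

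One minus Kaplan-Meier is 1 − Π(1 − d/r), where d is the number of new responders and r the number at risk. After each scan r falls by responders plus exits. Cumulative incidence is 30/43 in every row.

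| Exits | 1 − Kaplan-Meier | Result | Excess over 69.8% |
|---|---|---|---|
| 0 | 1 − (28/43)(18/28)(13/18) | 69.8% | 0 |
| 2 | 1 − (28/43)(17/27)(11/16) | 71.8% | 2.0 points |
| 4 | 1 − (28/43)(16/26)(9/14) | 74.2% | 4.5 points |
| 6 | 1 − (28/43)(15/25)(7/12) | 77.2% | 7.4 points |
| 8 | 1 − (28/43)(14/24)(5/10) | 81.0% | 11.2 points |

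A different split of responses over the scans changes the size but not the sign.

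**Response duration at 2 years**

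Let R be the observed incidence of relapse or progression among responders by 2 years, and D the incidence of death without relapse. Assume constant cause-specific hazards and that duration is analysed by Kaplan-Meier.

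- Death as an event: 1 − R − D.
- Death censored: the total hazard is −ln(1 − R − D), of which relapse takes the share R/(R + D). Kaplan-Meier is therefore (1 − R − D)^(R/(R+D)).
- Relapse-free with death competing: 1 − R.

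| D | Death censored (R = 20%) | Death as event (R = 20%) | Excess (R = 20%) | Excess for R = 10% to 30% |
|---|---|---|---|---|
| 0% | 80.0% | 80.0% | 0 | 0 |
| 2% | 79.8% | 78.0% | 1.8 | 1.7 to 1.9 |
| 5% | 79.4% | 75.0% | 4.4 | 4.1 to 4.7 |
| 10% | 78.8% | 70.0% | 8.8 | 8.2 to 9.4 |

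Against 1 − R the sign reverses: Kaplan-Meier with deaths censored is 0 to 1.8 points lower over the same grid.

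A small count shows the same ordering. Take 40 responders, 3 early deaths in remission and 6 later relapses. Censoring the deaths gives 31/37 = 83.8%. Counting them as events gives 31/40 = 77.5%. One minus the cumulative incidence of relapse gives 34/40 = 85.0%.

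**The case against.** A reader might infer that the plan does censor failures and deaths, so that both summaries are bound to be too favourable. The documents do not support that. They state no censoring rule and no analysis set for time to response, and name no estimator for duration. The one explicit censoring rule nearby is for post-transplant relapse, where death already competes. If time to response is summarised in responders only, failures are not in the analysis and the bias does not arise. For duration, the direction depends on the comparator, as the 85.0% against 83.8% above shows. All of this stands, and the point is therefore conditional.

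Exits may also be few. Sections 1 and 12.1.1 send week-6 progressors, and patients not in CR at week 12, on to NIVO + ICE, so neither is in itself an exit. A patient followed without CR to the week-18 scan is in every risk set and adds no bias. Cohort B schedules one PET-CT, at the end of week 8, with an optional further cycle, which leaves little room for censoring between scans. This also stands: the effect is mainly a Cohort A matter and may be near the lower end of the range.

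Finally, deaths in remission remain visible in PFS and in non-relapse mortality. That limits the harm, but it does not give the two response summaries a rule of their own. For time to response, moreover, the plan has named a method that is biased upward whenever exits before response are censored.

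**Conclusion.** The point holds in conditional form.

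- **Time to response.** Kaplan-Meier on all treated patients, with failures censored, overstates the proportion responding by about 2 points with 2 exits of 43 and about 11 points with 8. It does so by nothing if there are no exits. The counts are assumed.
- **Response duration.** If analysed by Kaplan-Meier with deaths in remission censored, 2-year durability looks about 2 points better than a death-as-event definition at 2% deaths without relapse, and 8 to 9 points better at 10%. This rests on constant hazards and assumed rates. It is not an overstatement relative to the cumulative incidence of relapse.

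It would be wrong to carry this over to the main results. The primary CR rate is a proportion with Clopper-Pearson limits, the Simon rules use CR counts, and PFS counts death. None of these changes. This is a minor but worthwhile correction.

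**What to change.** In Section 12.4, define time to response and its analysis set. Estimate it by cumulative incidence, with death, discontinuation of protocol therapy and start of other therapy before response as competing events. Alternatively, state that it describes responders only.

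In Section 11.1, end duration of response and duration of CR at relapse, progression or death from any cause, whichever comes first. Name the estimator and state the censoring rule for patients alive without relapse.

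The cost is a few sentences. The competing-risks method is already cited in Section 12.4, and dates of progression and death are already needed for PFS and overall survival. No new data and no change in sample size are required.

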12.5 Analysis of Correlative Endpoints

Because of the limited sample size inherent to phase II studies, the analysis of correlative endpoints is primarily exploratory. Standard descriptive methods will be used to summarize: 1) the role of PDL1/L2, CD68 on lymphoma specimens and 2) the role of T/B/NK cell subsets in the peripheral blood. If nivolumab or NIVO + ICE is not found to have sufficient activity, these patterns may help explain the lack of activity. If sufficient activity is found, then participants who experience an objective response will be compared to those who did not in terms of correlates. Estimates of variation will also prove useful for future clinical research on this regimen. Formal testing of these comparisons is not planned. All analysis will clearly document the exploratory nature of these studies, although no attempt will be made to adjust for multiple comparisons inherent in correlative studies.

13 Data Handling, Data Management, Record Keeping

13.1 Source Documents

Source documents are original documents, data, and records (e.g., medical records, pharmacy dispensing records, recorded data from automated instruments, laboratory data) that are relevant to the clinical trial. The Site Investigators or their designee will prepare and maintain adequate and accurate source documents. These documents are designed to record all observations and other pertinent data for each patient enrolled in this clinical trial. Source documents must be adequate to reconstruct all data transcribed onto the case report forms.

12.2 Data Capture Methods and Management

Data for this trial will be collected using Medidata RAVE, City of Hope's electronic capture system. Medidata RAVE is a web based, password protected system that is fully compliant with global regulatory requirements, including 21CRF Part 11 compliant.

Study personnel at each site will enter data from source documents corresponding to a subject's visit into the protocol-specific electronic Case Report Form (eCRF). A system of computerized data validation checks will be implemented and applied to the database on a regular basis. Queries are entered, tracked, and resolved through the EDC system directly. The study database will be updated in accordance with the resolved queries. All changes to the study database will be documented.

The Data Coordinating Center will run monthly data expectation reports that will list any outstanding and overdue data. The Data Coordinating Center will send via email to the participating site a report monthly on any missing and/or overdue data forms. The participating site will be required to complete the missing and/or overdue data forms within 1 week of receipt of the report.

Query reports will be generated on a monthly basis by the Data Coordinating Center. The Data Coordinating Center will send via email to the participating site a report monthly on any outstanding queries.

The participating site staff (whether the Principal Investigator or the staff collecting data at site) are required to take an eLearning Module within Medidata RAVE in order to obtain full access. The participating site staff will receive training via teleconference by COH DCC staff to review eCRFs that are specific to this protocol. Continuous training will be offered to participating sites if any amendments affect changes to the eCRFs during the course of the trial. The eCRFs within Medidata RAVE for this trial will have detailed instructions in the form of Help Text that provide instructions for completing each required field on each form.

12.3 Case Report Forms/Data Submission Schedule

Study personnel at each site will enter data from source documents corresponding to a subject's visit into the protocol-specific electronic Case Report Form (eCRF) when the information corresponding to that visit is available.

The Investigator is responsible for all information collected on subjects enrolled in this study. All data collected during the course of this study must be reviewed and verified for completeness and accuracy by the Investigator. All case report forms must be completed by designated study personnel. The completed case report forms must be reviewed, signed and dated by the Site Investigator or designee in a timely fashion.

All data will be collected using the electronic data collection system described in **Section 12.2**, and will be submitted according to the timelines indicated in Table 12.3.1.

All data will be collected within 1-2 weeks using standard Medidata Electronic Data Capture (EDC) case report forms. Data will be collected and stored on secure computers as indicated in **Section 12.2**. After 2 years, we will access the COH CIBMTR data repository to retrieve data regarding post-HCT long-term outcomes through study termination.

Table 12.3.1 Data Submission Schedule

| Form | Submission Timeline |
|---|---|
| Eligibility Checklist | Complete prior to registration |
| On Study Forms | Within 10 business days of registration |
| Baseline Assessment Forms | Within 10 business days of registration |
| Treatment Forms | Within 10 business days of treatment administration |
| Adverse Event Report Forms | Within 5 business days For transplant patients: within 10 business days of the end of evaluation period. |
| Response Assessment Forms | Within 10 business days of response assessment |
| Other assessment forms (e.g., concomitant meds, transplant data including mobilization, etc.) | Within 10 business days of the assessment |
| Transplant Core Intake Form | Within 10 business days of stem cell infusion |
| Post Transplant Disease Assessment Form | Within 14 days of the end of evaluation period |
| Off Treatment/Off Study Forms | Within 10 business days of completing treatment or being taken off study for any reason |
| Follow up/Survival Forms | Within 10 business days of the protocol defined follow up visit date or call |

12.4 Regulatory Records

The Investigator will maintain records, including updating records in accordance with Good Clinical Practice guidelines and FDA regulations. Additional information regarding required documents is provided in the DCC Operations Manual, a supplement to this protocol.

14 Adverse Events and Unanticipated Problems

The research team is responsible for classifying AEs and UPs as defined in the relevant regulations and reporting to all applicable parties, including but not limited to the COH IRB, DSMC, Food and Drug Administration (FDA), National Institutes of Health (NIH) and other collaborators, e.g., pharmaceutical companies. The research team is responsible for the continued monitoring and tracking of all AEs in order to ensure non-reportable events are reviewed and monitored and do not rise to a reporting level.

14.1 Assessment of Adverse Events

The site Investigator will be responsible for determining the event name, assessing the severity (i.e. grade), expectedness, and attribution of all adverse events as applicable per the [City of Hope Clinical Research Adverse Event and Unanticipated Problem policy](#). Adverse events will be characterized using the descriptions and grading scales found in the most recent version of CTCAE version 4.03. A copy of the scale can be found at https://evs.nci.nih.gov/ftp1/CTCAE/CTCAE_4.03/CTCAE_4.03_2010-06-14_QuickReference_8.5x11.pdf. The determination of severity for all other events not listed in the CTCAE version 4.03 should be made by the investigator based on medical judgment.

The following definitions will be used to determine the causality (attribution) of the event to the study agent or study procedure.

- **Unrelated** -The event is clearly NOT related to study treatment, and is clearly related to other factors such as the participant's clinical state, other therapeutic interventions, or concomitant medications administered to the participant..
- **Unlikely** -The event is unlikely related to the study treatment, and is most likely related to other factors such as the participant's clinical state, other therapeutic interventions, or concomitant drugs.
- **Possible** -The event may be related to study treatment, as it follows a reasonable temporal sequence from the time of drug administration, but could have been produced by other factors such as the participant's clinical state, other therapeutic interventions, or concomitant drugs.
- **Probable** - The event is most likely related to study treatment, as it follows a reasonable temporal sequence from the time of drug administration, and follows a known response pattern to the study drug, and is unlikely related to the participant's clinical state, therapeutic interventions, or concomitant drugs.
- **Definite** - The event is clearly related to study treatment, as it follows a reasonable temporal sequence from the time of drug administration and a known response pattern to the study drug, and is not reasonably explained by other factors such as the participant's condition, therapeutic interventions, or concomitant drugs.

14.2 Reporting of Adverse Events

14.2.1 Routine Recording of Non-Serious Adverse Events

Routine AE recording will occur via data entry into the study eCRF. Recording of adverse events will begin once the patient is consented and will continue until 100 days after discontinuation of dosing. Adverse events will be monitored by the Protocol Management Team (PMT). Adverse events that do not meet the criteria of serious OR are not unanticipated problems do not require expedited reporting. AEs reported

through expedited processes (i.e. reported to the IRB, DSMC, FDA, etc.) must also be reported in routine study data submissions.

14.2.2 Expedited Reporting Requirements of SAEs and UPs to the COH Regulatory Committees

Adverse Events that meet the criteria of serious OR are unanticipated problems will be reported according to the approved [City of Hope Clinical Research Adverse Event and Unanticipated Problem policy](#).

Reporting of SAEs will begin after the patient signs the study consent, and must be followed until the event is resolved, stabilized, or determined to be irreversible by the participating investigator. Follow-up SAE reports must be submitted for all events that require expedited reporting when the status of the event changes and until the resolution or stabilization of the event. For ongoing reportable adverse events that are unrelated to study agent, the follow-up period may end at the 30-days post study-drug assessment.

Non COH Sites:

Serious Adverse Events meeting the criteria specified in the City of Hope Clinical Research Adverse Event and Unanticipated Problem policy will be reported to the Data Coordinating Center (DCC) and Study PI within **24 hours** of notification that the event occurred.

Procedure for reporting SAEs/UPs to the COH DCC

1. Sites are to report to their local IRB per their site's specific institutional and IRB guidelines. As soon as possible, non-COH sites will provide to the COH DCC copies of the IRB submission and corresponding IRB response.
2. Document/describe the SAE/UP on each of the following:
 - a. MedWatch 3500A: Downloadable form at <http://www.fda.gov/medwatch/getforms.htm>
 - b. UP/SAE Coversheet (Appendix B): A modifiable Microsoft Word document is available from the DCC. An electronic signature on the document will be accepted.
3. Scan and email above documents to [contact] and [contact] with the subject title as "COH IRB 16403 SAE". If an email receipt from Coordinating Center personnel is not received within one working day, please email [contact].

